2.5.3 Handling of missing values/censoring/discontinuations

For the primary analysis, patients with missing baseline spleen length will be excluded from the analysis as change from baseline cannot be calculated.

Patients with missing spleen length at Week 24 or who withdraw earlier from the study will be considered as a non-responder.

2.5.4 Supportive and Sensitivity analyses

The primary analysis (as described in Section 2.5.2) will also be repeated on the PPS. Furthermore, the primary endpoint will be analyzed on patients with non-missing spleen length at both baseline and Week 24. Proportion of patients achieving a 50% reduction in spleen length

at any time during the study will also be reported along with corresponding exact 95% confidence interval using Clopper and Pearson exact method.

IWG-MRT response criteria will also be used to analyze spleen length response rate at Week 24. Response as per IWG-MRT criteria is defined as follows:

- A baseline splenomegaly that is palpable at 5-10 cm, below the LCM at baseline, becomes not palpable, post-baseline or
- A baseline splenomegaly that is palpable at >10 cm at baseline, below the LCM, decreases by $\geq 50\%$, post-baseline
- A baseline splenomegaly that is palpable at <5 cm at baseline, below the LCM, is not eligible for spleen response

Patients meeting response criteria as per above definition will be considered as responders or else will be non-responders. The point estimate of the proportion of responders along with corresponding exact 95% confidence interval using Clopper and Pearson exact method will be presented at Week 24. The same analysis will be repeated for proportion of responders as per IWG-MRT response criteria for spleen at any time during the study.

2.6 Analysis of the key secondary objective

There is no key secondary objective for this study.

2.7 Analysis of secondary efficacy objective(s)

All secondary efficacy analyses will be performed on the FAS unless otherwise specified.

2.7.1 Secondary endpoints

The secondary efficacy variables for this study are:

- the proportion of patients achieving a 50% reduction in spleen length at Week 48
- percent change from baseline in spleen length over time
- summary of transfusions over time

2.7.2 Statistical hypothesis, model, and method of analysis

The spleen length response rate at Week 48 will be evaluated. The point estimate of the proportion of patients achieving $\geq 50\%$ reduction in spleen length at Week 48 along with corresponding exact 95% confidence interval using Clopper and Pearson exact method will be presented.

Percent change from baseline in spleen length over time will be evaluated to assess the effect of ruxolitinib on spleen length. The analysis will be performed for each visit and at end of treatment. This parameter is computed by dividing the difference of spleen length at assessment time and at baseline by the length at baseline multiplied by one hundred.

To evaluate the effect of ruxolitinib on transfusion requirements, the following will be summarized:

- Number and percentage of transfusions over time
- Proportion of patients who are transfusion dependent (TD). Transfusion dependence is defined as per IWG-MRT criteria: 6 or more units of transfusion in 12 weeks prior to baseline.
- For transfusion dependent (TD) patients at baseline, the following will be analyzed:
 - transfusion independence (TI) rate (requiring no unit of transfusion for ≥ 12 weeks at any time during the study)
 - transfusion response rate (not TD: having 5 or less units of transfusion for ≥ 12 weeks at any time during the study)
- For patients who were not transfusion dependent (TD) at baseline, the following will be analyzed:
 - transfusion dependence (TD) rate (requiring 6 or more units of transfusion for ≥ 12 weeks at any time during the study)

2.8 Safety analyses

For all safety analyses, the Safety set will be used, unless specified otherwise.

2.8.1 Adverse events (AEs)

AE summaries will include all AEs occurring during on-treatment period. All AEs collected in the AE eCRF page will be listed along with the information collected on those AEs e.g. AE relationship to study drug, AE outcome etc. AEs starting during the post-treatment period will be flagged in the listings.

AEs will be summarized by number and percentage of subjects having at least one AE, having at least one AE in each primary system organ class (SOC) and for each preferred term (PT) using MedDRA coding. A subject with multiple occurrences of an AE will be counted only once in the respective AE category. A subject with multiple CTCAE grades for the same preferred term will be summarized under the maximum CTCAE grade recorded for the event. AE with missing CTCAE grade will be included in the 'All grades' column of the summary tables.

In AE summaries the primary system organ class will be presented alphabetically and the preferred terms will be sorted within primary SOC in descending frequency.

The following adverse event summaries will be produced by treatment; overview of adverse events and deaths (number and % of subjects who died), with any AE, any SAE, AEs by SOC and PT, summarized by relationship (all AEs and AEs related to study treatment), seriousness (SAEs and non-SAEs), leading to treatment discontinuation (drug withdrawn), leading to dose interruption/adjustment (dose increased or dose reduced), requiring additional therapy (concomitant medication or non-drug therapy) and leading to fatal outcome. In addition, a summary of serious and non-serious adverse events with number of occurrences will be produced (an occurrence is defined as >1 day between start and prior end date of record of same preferred term) as per EudraCT requirements.

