Considering the typical hemoglobin level for many MF patients is already at the Grade 0/Grade 1 border (hemoglobin of 10 g/dL), assessment of a dose regimen that might provide clinically meaningful symptomatic and spleen size reduction benefits of ruxolitinib while lessening the degree of worsening hemoglobin levels is warranted.

Current label recommendation on starting doses in MF are 5, 15 or 20 mg BID, depending on platelet counts $50-100 \times 10^9/L$, $100-200 \times 10^9/L$ or $>200 \times 10^9/L$ respectively, regardless of hemoglobin level at baseline.

There is increasing literature suggesting the use of lower starting doses with up titrations depending on safety and efficacy in patients with anemia ([Tabarroki 2013](#), [Cervantes 2014](#), [Reilly 2014](#), [Harrison 2013](#), [Ho 2015](#)).

This multicenter phase II open label single arm study proposes to prospectively evaluate a starting dose of ruxolitinib 10 mg BID for 12 weeks with subsequent up titrations of 15mg BID and 20 mg BID in anemic myelofibrosis patients defined as a baseline hemoglobin < 10 g/dL (Please see [Figure 6-1](#) for details). The trial will evaluate if this alternative dosing approach achieves spleen reduction and symptom improvement to levels consistent with those reported in previous clinical trials but with an improved tolerability assessed by incidence of adverse events and transfusion requirements.

[figure not shown]
[figure not shown]

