7.1.3 Treatment period

Following completion of screening procedures and verifying patient eligibility, the patient will be approved for treatment via the IRT.

[figure not shown]
The study treatment phase begins on Day 1 with the first administration of ruxolitinib and will continue until 48 weeks after Last Patient First Treatment date or the patient is discontinued for other reasons as indicated in [Section 7.1.4](#).

Patients will be assessed as per visit schedule in [Table 7-1](#).

Visit windows of ± 7 days from scheduled study assessments will apply from Week 4 visit up to Week 24 and ± 14 days for visits after Week 24.

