10.5.3.2 Adverse events (AEs)

Summary tables for adverse events (AEs) will include only AEs that started or worsened during the on-treatment period, the *treatment-emergent* AEs.

The incidence of treatment-emergent adverse events (new or worsening from baseline) will be summarized by system organ class and or preferred term, severity (based on CTCAE grades), type of adverse event, relation to study treatment.

Serious adverse events, non-serious adverse events and adverse events leading to treatment discontinuations during the on-treatment period will be tabulated.

All deaths (on-treatment and post-treatment) will be summarized by system organ class and preferred term.

All AEs, deaths and serious adverse events (including those from the pre and post-treatment periods) will be listed and those collected during the post-treatment period will be flagged.

AEs will be assessed according to the Common Terminology Criteria for AEs (CTCAE version 4.03). AEs will be coded using the latest MedDRA terminology version during the time of data analyses.

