4.8 Undesirable effects

Summary of the safety profile

The safety assessment was based on a total of 855 patients (with MF or PV) receiving Jakavi in phase 2 and 3 studies.

Myelofibrosis

In the randomised period of the two pivotal studies, COMFORT-I and COMFORT-II, the median duration of exposure to Jakavi was 10.8 months (range 0.3 to 23.5 months). The majority of patients (68.4%) were treated for at least 9 months. Of 301 patients, 111 (36.9%) had a baseline platelet count of between 100,000/mm³ and 200,000/mm³ and 190 (63.1%) had a baseline platelet count of >200,000/mm³.

In these clinical studies, discontinuation due to adverse events, regardless of causality, was observed in 11.3% of patients.

The most frequently reported adverse drug reactions were thrombocytopenia and anaemia.

Haematological adverse drug reactions (any Common Terminology Criteria for Adverse Events [CTCAE] grade) included anaemia (82.4%), thrombocytopenia (69.8%) and neutropenia (16.6%).

Anaemia, thrombocytopenia and neutropenia are dose-related effects.

The three most frequent non-haematological adverse drug reactions were bruising (21.3%), dizziness (15.3%) and headache (14.0%).

The three most frequent non-haematological laboratory abnormalities were raised alanine aminotransferase (27.2%), raised aspartate aminotransferase (19.9%) and hypercholesterolaemia (16.9%). In phase 3 clinical studies in MF, neither CTCAE grade 3 or 4 hypercholesterolaemia, raised aspartate aminotransferase nor CTCAE grade 4 raised alanine aminotransferase were observed.

Long-term safety: As expected with an extended follow-up period, the cumulative frequency of some adverse events increased in the evaluation of the 3-year follow-up safety data (median duration of exposure of 33.2 months in COMFORT-I and COMFORT-II for patients initially randomised to ruxolitinib) from 457 patients with myelofibrosis treated with ruxolitinib during the randomised and extension periods of the two pivotal phase 3 studies. This evaluation included data from patients that were initially randomised to ruxolitinib (N=301) and patients that received ruxolitinib after crossing over from control treatment arms (N=156). With these updated data, therapy discontinuation due to adverse events was observed in 17.1% of patients treated with ruxolitinib.

Polycythaemia vera

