2. on-treatment period: from date of first administration of study treatment to 30 days after date of last actual administration of any study treatment (including start and stop date)
3. post-treatment period: starting at day 30+1 after last administration of study treatment.

Safety summaries (tables, figures) include only data from the on-treatment period with the exception of baseline data which will also be summarized where appropriate (e.g. change from baseline summaries). In addition, a separate summary for death including on-treatment and post-treatment deaths will be provided. In particular, summary tables for adverse events (AEs) will summarize only on-treatment events, with a start date during the on-treatment period (treatment-emergent AEs).

However, all safety data (including those from the pre- and post-treatment period) will be listed and those collected during the post-treatment period will be flagged.

Analysis Visit Windows

In order to summarize data collected over time (including unscheduled visits), the assessments will be time slotted. The following general rule will be applied in creating the assessment windows: If more than one assessment is done within the same time window, the assessment performed closest to the target date will be used. If 2 assessments within a time window are equidistant from the target date, then the earlier of the 2 assessments will be used. If there are multiple assessments on the same date, then the worst case will be used. Data from all assessments (scheduled and unscheduled), including multiple assessments, will be listed.

Analysis Visit windows

Assessment	Target day of assessment	Time Interval
Baseline	1	≤ Day 1
Week 4	28	Day 2 to day 42
Week 8	56	Day 43 to day 70
Week 12	84	Day 71 to day 98
Week 16	112	Day 99 to day 126
Week 20	140	Day 127 to day 154

Week 24	168	Day 155 to day 210
Week 36	252	Day 211 to day 294
Week 36+(12*k)	d=k*84+252, k=1,2,3,etc.	Day d-41 to day d+42

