2.8.1.1 Adverse events of special interest / grouping of AEs

An adverse event of special interest is a grouping of adverse events that are of scientific and medical concern specific to compound INC424. These groupings are defined using MedDRA terms, SMQs (standardized MedDRA queries), HGLTs (high level group terms), HLT (high level terms) and PTs (preferred terms). Customized SMQs (Novartis MedDRA queries, NMQ) may also be used. A NMQ is a customized group of search terms which defines a medical concept for which there is no official SMQ available or the available SMQ does not completely fit the need. It may include a combination of single terms and/or an existing SMQ, narrow or broad. For each specified AESI, number and percentage of patients with at least one event of the AESI occurring during on treatment period will be summarized.

A Case Retrieval Sheet (CRS; an Excel file) with the exact composition of the adverse events groupings is to be used to map reported adverse events to the AESIs groupings (termed Specific Event Categories (SECs) in the CRS). This file may be updated (i.e. it is a living document) based on review of accumulating trial data. The latest version of the CRS document available at the time of the analyses will be used.

A listing of all grouping levels down to the MedDRA preferred terms used to define each AESI will be generated.

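### AE and AESI percentages are taken over follow-up that depends on accrual length; add incidence within fixed windows (Weeks 0-12, 0-24, 0-48)

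*SAP*

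**What the plan says.** **Measure.** SAP 2.8.1: "AEs will be summarized by number and percentage of subjects having at least one AE", overall and by system organ class and preferred term. SAP 2.8.1.1, for each AESI: "number and percentage of patients with at least one event of the AESI occurring during on treatment period will be summarized". One further table goes beyond percentages: "a summary of serious and non-serious adverse events with number of occurrences will be produced". It has no exposure denominator. Protocol 10.5.3.2 is similar: "The incidence of treatment-emergent adverse events (new or worsening from baseline) will be summarized by system organ class and or preferred term".

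**Counting period.** SAP 2.1.1 defines the "on-treatment period: from date of first administration of study treatment to 30 days after date of last actual administration of any study treatment". It is not cut at a common week.

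**Length of follow-up.** Protocol 7.1.3 says treatment "will continue until 48 weeks after Last Patient First Treatment date". Section 4.1 gives the same rule, 6.1.5 calls 48 weeks a planned minimum, and Table 7-1 schedules visits at Weeks 60, 72, 84 and beyond. Protocol 2.2, however, describes treatment for 48 weeks.

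**Purpose.** Protocol 2.1 looks for spleen and symptom results in line with earlier trials, "but with an improved tolerability assessed by incidence of adverse events and transfusion requirements". Protocol 2.6 names lower rates of cytopenias and transfusion as the main potential benefit. Appendix 6, section 4.8, reports that in the pivotal myelofibrosis trials "the median duration of exposure to Jakavi was 10.8 months", with a range of 0.3 to 23.5 months.

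**The concern.** The proportion of patients with at least one event grows with time observed. Here that time is set by a calendar date, so early enrollees can be observed for longer than late ones. Two runs of this trial with identical risk but different accrual speed would report different AE percentages.

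The trial has one arm, so earlier trials are the only reference for the tolerability aim. The protocol's own background shows that exposure matters. Appendix 6, section 4.8, says cumulative AE frequency rose with longer follow-up in the myelofibrosis trials. For the polycythaemia vera trial it says the same, while exposure-adjusted rates stayed broadly comparable. Protocol 1.2.1.2.3 mentions a patient-year adjustment for headache and dizziness in the earlier myelofibrosis trials. The SAP plans no AE incidence at a common week, no rate per patient-time and no time-to-first-event summary. A difference from the earlier trials could then reflect length of observation rather than the lower starting dose. The AE tables also do not isolate the first 12 weeks, when that starting dose is in use.

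**Working it through.** The documents give no numerical basis for the AE analysis, so there is no planned figure to reproduce on this point. The design figures for spleen response (13 of 50: posterior probability 0.0243; success probability 0.0301 at a true rate of 15% and 0.9339 at 35%) recompute exactly and do not depend on it.

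**Inputs from the documents**
- Reference event: 11.3% of patients (discontinuation for AEs in the pivotal trials, Appendix 6, 4.8), used only as an example of an event of that frequency.
- Reference exposure: median 10.8 months.
- Minimum potential follow-up: T = 48 weeks = 48 × 7 / 30.4375 = 11.04 months.

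**Assumptions, because the documents give no figure**
- Accrual uniform over A months, with A from 0 to 24.
- Discontinuation d of 0 or 0.03 per month.
- Constant hazard; the 30-day tail is ignored; median exposure stands in for the whole exposure distribution.

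**Step 1, hazard.** h = −ln(1 − 0.113) / 10.8 = 0.0111 per month, or 13.3 per 100 patient-years.

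**Step 2, crude percentage for a patient with potential follow-up t.** h/(h + d) × [1 − exp(−(h + d)t)], averaged over t uniform between T and T + A.

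| Accrual A (months) | 11.3% event, no dropout | 11.3% event, 3%/month | 20% event, no dropout | 20% event, 3%/month |
|---|---|---|---|---|
| 0 | 11.5% | 9.9% | 20.4% | 17.5% |
| 6 | 14.4% | 11.8% | 25.1% | 20.7% |
| 12 | 17.2% | 13.5% | 29.5% | 23.3% |
| 18 | 19.8% | 14.9% | 33.5% | 25.5% |
| 24 | 22.3% | 16.1% | 37.2% | 27.3% |

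Risk is the same in every row. The crude figure falls below or rises above the reference depending on two quantities that the plan does not fix.

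**Step 3, the Week 24 data cut.** Potential follow-up then runs from 24 weeks (5.52 months) to 24 weeks + A. Without dropout, the 11.3% event reads 5.9% (A = 0), 11.9% (A = 12) or 17.4% (A = 24).

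**Step 4, does a patient-year rate cure this?** Appendix 6, 4.8, gives a second figure: 17.1% at a median of 33.2 months, in a set that also includes crossover patients. The implied rate is −ln(1 − 0.171) / 33.2 × 1200 = 6.8 per 100 patient-years, against 13.3 above. The percentage rose about 1.5-fold while the rate roughly halved. With a constant hazard the later percentage would have been 1 − exp(−0.0111 × 33.2) = 30.8%, not 17.1%. So, with the change in patient set as a caveat, the hazard appears to fall. A whole-period rate then also depends on follow-up, in the opposite direction.

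**The case against.** **No AE comparison is a planned analysis.** The safety objective is descriptive, SAP 2.8 has no historical comparator, and the success rule concerns the spleen alone. This stands: the comparison comes from the stated purpose in protocol 2.1 and 2.6. Protocol 2.2 puts it in terms of early hemoglobin and platelet declines and transfusions, for which SAP 2.8.3 and 2.7.2 already plan summaries over time.

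**The earlier trials also had variable exposure.** Their range was 0.3 to 23.5 months, and their median of 10.8 months is about 47 weeks, close to the 48-week minimum here. A reader might infer that the two sets of percentages cannot be compared at all. The documents do not support that: with 6 months' accrual and 3% monthly discontinuation, the example reads 11.8% against 11.3%.

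**Cytopenias come early.** Protocol 1.2.1.2.3 places about half of grade 3/4 anemia and thrombocytopenia in the first 8 weeks of COMFORT-I. Appendix 6, 4.8, gives median onset of 1.5 months for grade 2 or higher anaemia, about 8 weeks for grade 3/4 thrombocytopenia and 12 weeks for grade 3/4 neutropenia. Later follow-up should add fewer such events than a constant hazard implies. This stands. The point matters more for events that accumulate later and for discontinuation due to AEs. The worst post-baseline laboratory grade in SAP 2.8.3 shares the weakness.

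**Other output helps the reader.** Occurrence counts, AE listings and exposure by duration category (SAP 2.4.1) are planned. They help interpretation, but none gives incidence over a common period.

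**Sampling error is large.** With 6 of 50 patients (12%), the exact 95% interval is 4.5% to 24.3%, as wide as much of the distortion shown. That calls for intervals; it does not make the accrual effect harmless.

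**Conclusion.** The point holds as a weakness in how AEs are summarised, not as a flaw in a planned test. On the treatment rule in protocol 4.1, 6.1.5 and 7.1.3, the percentages in SAP 2.8.1 and 2.8.1.1 depend on accrual length and discontinuation. The tolerability aim in protocol 2.1 is then harder to interpret. In the example, 11.3% becomes anything from 9.9% to 22.3% with no change in risk, assuming a constant hazard, uniform accrual over 0 to 24 months and 0 to 3% monthly discontinuation.

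A reader might infer a steeper effect: a 40% event at 48 weeks reaches 1 − 0.6^1.5 = 54% at 72 weeks and 1 − 0.6² = 64% at 96 weeks. Those are figures for a patient actually followed that long. Under uniform accrual, a mean potential follow-up of 72 weeks needs 48 weeks of accrual, and 96 weeks needs 96. The figures also assume no dropout and a constant hazard, which the early onset of cytopenias contradicts. Nor do the documents support the reading that the bias always inflates: it can go either way.

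Protocol 2.2 and the sections just named differ on treatment length and must be reconciled. If follow-up were the same for all patients, only the A = 0 row would apply and the accrual part of the problem would disappear.

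**What to change.** Add to SAP 2.8.1 and 2.8.1.1: the number and percentage of Safety Set patients with a treatment-emergent AE (all grades; grade 3-4; leading to discontinuation), and with each AESI group, within Weeks 0-12, 0-24 and 0-48, with 95% confidence intervals. Name these tables as the basis for any comparison with earlier trials, and state the exposure basis of each earlier-trial figure used.

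Two practical notes. The 0-48 window is complete for all patients only at the final analysis; the two shorter windows can be reported at the primary analysis. Fixed windows remove the dependence on accrual but not on early stopping, so show how many patients were still on treatment at the end of each window.

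Rates per 100 patient-years may be added as a supplement, with a note that they too vary with follow-up when hazards fall. The existing whole-period tables can stay.

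Cost: a few extra tables from AE dates already collected, and a short SAP edit. No new data are needed.
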